**11.5.4. Safety**

**11.5.4.1. Exposure**

**Exposure**

**Exposure and Post-treatment Duration**

- Duration of exposure to study treatment is calculated as:
  - treatment stop date – treatment start date +1
- Duration of post-treatment time spent on study is calculated as:
  - study conclusion date – treatment stop date
- Duration of total time spent on study is calculated as:
  - study conclusion date – treatment start date + 1

**Exposure Categories**

- The following exposure categories will be derived:  
 ≥1 day, ≥4 weeks, ≥8 weeks, ≥12 weeks, ≥16 weeks, ≥20 weeks, ≥24 weeks, ≥28 weeks, ≥32 weeks, ≥36 weeks, ≥40 weeks, ≥44 weeks, ≥48 weeks and ≥52 weeks. An additional category of 51-53 weeks will also be summarized.
- For post-treatment duration, the following categories will be derived:  
 0 days, 1-7 days, >7 days

**11.5.4.2. Adverse Events**

**Adverse Events**

**Adverse Event Rate**

- The event rate per thousand subject-years will be displayed on most AE data displays listed in Section 11.12 (including summaries of AESIs and Serious Adverse Reports). Event rate per thousand subject-years will be calculated as the number of events x 1000 divided by the at risk period during the time-period of interest as defined in Section 11.5.1.5.2.

Adverse Events of Special Interest (AESI)		

 
AESI have been defined as AEs which have specified areas of interest for FF, VI or UMEC or the overall COPD population. The following table presents the AESI groups. Groups which are not SMQs are made up of a selection of preferred terms (PTs) defined by GSK. The complete list, including the PTs which contribute to each of the groups will be provided by Global Clinical Safety and Pharmacovigilance (GCSP) using the MedDRA version current at the time of reporting. This will be finalized prior to unblinding.
 
		
AESI Group	AESI Subgroup	Sub-SMQ
Adrenal suppression		
Anticholinergic syndrome (SMQ)		
Asthma/bronchospasm (SMQ)		
Cardiovascular effects	Cardiac arrhythmia	Arrhythmia related investigations, signs and symptoms (SMQ)
		Bradycardia terms, nonspecific (SMQ)
		Conduction defects (SMQ)
		Disorders of sinus node function (SMQ)
		Cardiac arrhythmia terms, nonspecific (SMQ)
		Supraventricular tachyarrhythmias (SMQ)
		Tachyarrhythmia terms, nonspecific (SMQ)
		Ventricular tachyarrhythmias (SMQ)
	Cardiac failure (SMQ)	
	Ischaemic heart disease (SMQ)	
Hypertension (SMQ)		
Central nervous system haemorrhages and cerebrovascular conditions (SMQ)		
Ocular effects	Glaucoma (SMQ)	
	Lens disorder (SMQ)	
Decreased bone mineral density and associated fractures		
Effects on potassium		
Gastrointestinal obstruction (SMQ)		
Hyperglycaemia/new onset diabetes mellitus (SMQ)		
Hypersensitivity		
Local steroid effects		
Pneumonia		
Lower Respiratory Tract Infection (LRTI) excluding pneumonia		
Tremor		
Urinary retention		

Adverse Events Considered of Interest in the Elderly	

 
• AEs considered of interest in the elderly will be summarized by age category and overall for each treatment group.
 
• SMQs or PTs for these groupings are provided below.
 
	
AE Grouping	SMQ, PT or System Organ Class (SOC)
Any AE	
Serious AE	
Results in death	
Life-threatening	
Hospitalization/prolongs existing hospitalization	
Results in disability/incapacity	
Congenital anomaly/birth defect	
Other (medically significant)	
Possible drug-induced liver injury	
Adverse events leading to permanent discontinuation of study treatment or withdrawal from study	
Psychiatric disorders	Psychiatric disorders (SOC)
Nervous system disorders	Nervous system disorders (SOC)
Accidents and injuries	Accidents and injuries (SMQ)
Cardiac disorders	Cardiac disorders (SOC)
Vascular disorders	Vascular disorders (SOC)
Cerebrovascular disorders	Central nervous system vascular disorders (SMQ)
Infections and infestations	Infections and infestations (SOC)
Anticholinergic syndrome	Anticholinergic syndrome (SMQ)
Quality of life decreased	Quality of life decreased (PT)
Postural hypotension, Falls, Black outs/Syncope, Dizziness, Ataxia and Fractures	Postural hypotension (selected PTs*), Falls (PT), Black outs/Syncope (selected PTs*), Dizziness (selected PTs*), Ataxia (selected PTs*) and Fractures (selected PTs*)

* Preferred terms which contribute to each of the groups will be provided by GCSP using the MedDRA version current at the time of reporting. This will be finalised prior to unblinding.
	
Association to Serious Adverse Reports	

An event in the pneumonia AESI group is considered associated with an adjudicated Serious Adverse Report if the Serious Adverse Report was classified as 'COPD exacerbation with evidence of pneumonia' or 'Pneumonia/respiratory tract infection without COPD exacerbation' and the onset of the Serious Adverse Report is within -7 to +10 days of the onset of the pneumonia AESI.
	

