**9.2.3.1. Adverse Events of Special Interest**

Adverse events of special interest (AESI) have been defined as AEs which have specified areas of interest for FF, VI, or UMEC or for the COPD population. A list of Standardized Medical Dictionary for Regulatory Activities (MedDRA) Queries (SMQs) and other groupings for AESI is provided in Section [11.5.4.2](#).

A summary of AE categories of interest in the elderly by age and overall for each treatment group will be provided for AESI. The list of AE categories of interest in the elderly is provided in Section 11.5.4.2.

A summary of the number of events in the pneumonia AESI group and the number of these that had investigator-reported pneumonia (on the pneumonia eCRF form, and split by those supported/not supported by x-ray/CT scan) and/or that had an associated adjudicated report of pneumonia will be provided. This will be repeated for serious events in the pneumonia AESI group within the same table. The number of investigator-reported pneumonia events not reported as pneumonia AESI will also be provided and the number of adjudicated serious adverse reports of pneumonia not associated with a pneumonia AESI. Association between events in the pneumonia AESI group and adjudicated reports of pneumonia is defined in Section 11.5.4.2.

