3.028	ITT	Summary of Adjudicated On-treatment Serious Adverse Reports	SAC
3.029	ITT	Summary of Adjudicated On-treatment Non-fatal Serious Adverse Reports	SAC
3.030	ITT	Summary of Adjudicated On-treatment Fatal Serious Adverse Reports	SAC
3.031	ITT	Summary of Adjudicated Post-treatment Serious Adverse Reports	SAC
3.032	ITT	Summary of Adjudicated Post-treatment Non-fatal Serious Adverse Reports	SAC
3.033	ITT	Summary of Adjudicated Post-treatment Fatal Serious Adverse Reports	SAC
Adverse Events of Special Interest			
3.034	ITT	Summary of On-treatment Adverse Events of Special Interest	SAC [1]
3.035	ITT	Summary of On-treatment Adverse Events of Special Interest by Eosinophil Subgroup	SAC
3.036	ITT	Summary and Analysis of Time to First On-treatment Event in the Pneumonia AESI Group	SAC
3.037	ITT	Summary and Analysis of Time to First On-treatment Event in the Pneumonia AESI Group by Eosinophil Subgroup	SAC
3.038	ITT	Summary of Pneumonia Risk Factors at Screening for Subjects with an Event in the Pneumonia AESI Group	SAC
3.039	ITT	Summary of Pneumonia Risk Factors at Screening for Subjects with an Event in the Pneumonia AESI Group by Eosinophil Subgroup	SAC
3.040	ITT	Summary and Analysis of Time to First On-treatment Event in the Cardiovascular AESI Group	SAC
3.041	ITT	Summary of Incidence of On-treatment Pneumonia AESI and Adjudicated Pneumonia	SAC
Serious Adverse Events of Special Interest			
3.042	ITT	Summary of On-treatment Serious Adverse Events of Special Interest	SAC
3.043	ITT	Summary of On-treatment Fatal Serious Adverse Events of Special Interest	SAC
3.044	ITT	Summary and Analysis of Time to First On-treatment Event in the Pneumonia AESI Group Resulting in Hospitalization/Prolonged Hospitalization or Death	SAC

Safety Tables			
No.	Popu- lation	Title	Deliverable [Priority]
3.045	ITT	Summary and Analysis of Time to First On-treatment Event in the Cardiovascular AESI Group Resulting in Hospitalization/Prolonged Hospitalization or Death	SAC
MACE			
3.046	ITT	Summary of On-treatment Major Adverse Cardiac Events (MACE) – Narrow Definition	SAC
3.047	ITT	Summary of On-treatment Major Adverse Cardiac Events (MACE) – Broad Definition	SAC
Pneumonia (eCRF Pneumonia Form)			
3.048	ITT	Summary of On-treatment Pneumonia Incidence	SAC
3.049	ITT	Summary of On-treatment Details of Pneumonia	

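### SAP 11.5.4.2 accepts a mixed pneumonia/other-infection adjudication class as adjudicated pneumonia, so the Table 3.041 cross-check can count serious infections that are not pneumonia

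*SAP*

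**What the plan says.** SAP 11.5.4.2 defines when a pneumonia AESI and an adjudicated report belong together. The rule starts from an event already in the pneumonia AESI group and accepts a report from either of two adjudication classes. One class is for exacerbations that show evidence of pneumonia. The other is "Pneumonia/respiratory tract infection without COPD exacerbation". Besides the class, the rule looks only at timing, and requires that "the onset of the Serious Adverse Report is within -7 to +10 days of the onset of the pneumonia AESI". It has no other condition.

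SAP 9.2.3.1 uses this link in one summary. Among events in the pneumonia AESI group, it counts those with a pneumonia eCRF record (split by x-ray/CT support) "and/or that had an associated adjudicated report of pneumonia will be provided". The counts are repeated for serious events. The same summary also gives "the number of adjudicated serious adverse reports of pneumonia not associated with a pneumonia AESI". For the link between the two sources, 9.2.3.1 refers back to 11.5.4.2. The display is Table 3.041, "Summary of Incidence of On-treatment Pneumonia AESI and Adjudicated Pneumonia".

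Among adverse events the SAP keeps the two conditions apart: the AESI list in 11.5.4.2 has a pneumonia group and a separate group, "Lower Respiratory Tract Infection (LRTI) excluding pneumonia".

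**The concern.** Protocol 1.3.3 names pneumonia as a key risk of ICS-containing combinations, and two of the three arms contain FF. Table 3.041 is where the reader can see whether pneumonia events reported by investigators agree with an independent, blinded committee. If the adjudicated side of that comparison holds pneumonia together with other serious respiratory infections, but carries a pneumonia-only name, it can mislead in two ways. A serious lower respiratory infection that the investigator rightly did not call pneumonia can look like a missed pneumonia. A pneumonia AESI can also look confirmed by a report that was not about pneumonia.

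**Working it through.** The documents state no figure to reproduce. The check is to trace the rule through the SAP.

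**1. What the class can hold.** The first accepted class requires evidence of pneumonia. The second is mixed by name. Protocol 9.9 leaves the adjudication plan to a charter that is not among the documents, so whether the mixed class is subdivided is unknown.

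**2. How the rest of the plan treats the distinction.** Protocol 6.2.4.1 classifies lower respiratory tract infection (acute bronchitis is its example) separately from pneumonia. Protocol 6.3.16 asks for a new infiltrate plus at least two signs or symptoms to confirm pneumonia. SAP 11.5.4.7 counts pneumonia as x-ray-supported only when an associated film shows infiltrates. The adjudication class is not held to this distinction.

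**3. Three cases passed through the rule.**

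- *Serious bronchitis, adjudicated into the mixed class, no pneumonia AESI within the window.* The linked counts do not change, because the rule starts from an event already in the pneumonia AESI group. The unlinked count rises by one if the two classes define it. 9.2.3.1 offers no other definition of an adjudicated report of pneumonia, so this is the natural reading, but it is an inference.
- *Non-serious pneumonia AESI, with a different serious respiratory infection, adjudicated into the mixed class, starting within the next 10 days.* No event is added, but the AESI is now shown with an associated adjudicated report. Protocol 9.9 sends serious events to adjudication, so the pneumonia itself need not have been reviewed.
- *Serious pneumonia AESI, adjudicated as pneumonia into the mixed class.* The match is right, but in the table it cannot be told from a false match that involves another serious AESI.

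**4. Which analyses take the adjudication class as input.** SAP 9.2.13.2 to 9.2.13.5 define the Cox models: time to first pneumonia AESI, the version resulting in hospitalization or death, the eosinophil subgroup version, and the composites with exacerbations and cardiovascular events. All use AESI groups, and none uses an adjudication class. The pneumonia eCRF summaries (9.2.5) do not use it either.

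**5. Size.** The documents give no rate of serious pneumonia, no rate of serious non-pneumonia infection and no breakdown of the mixed class. Only an illustration on assumptions is possible. Let R be the true ICS to non-ICS ratio and f the share of the non-ICS arm's counted reports that are not pneumonia, with the same extra incidence in both arms. The observed ratio is then R(1 - f) + f. For R, take the all-pneumonia incidences in protocol 1.3.1 from the FF/VI program: 6% to 7% with FF/VI against 3% with VI alone, so 6/3 = 2.00 to 7/3 = 2.33.

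| f (assumed) | R = 2.00 | R = 2.33 |
|---|---|---|
| 10% | 1.90 | 2.20 |
| 25% | 1.75 | 2.00 |
| 50% | 1.50 | 1.67 |

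These ratios describe a comparison that the SAP does not plan. They show only the direction in which a count built from the mixed class would move if the other infections were equally frequent in both arms.

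**The case against.** The strongest reply is that this is a labelling matter in one descriptive table. The linked counts cannot gain events. The content of the class is set in a charter that has not been seen and may already separate pneumonia. The group for lower respiratory infection without pneumonia is a grouping of adverse-event terms, while the adjudication class is a committee's category, so the two need not coincide. The date window is the SAP's usual convention, also used to tie chest films to exacerbations and to pneumonia. Counts are repeated for serious AESIs, and x-ray/CT support is split out in the same table. For a safety risk, broad capture is the cautious choice.

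Most of this stands as a limit on scope. It does not answer the label: the SAP states the rule, gives no narrower definition, and reports a class that by its name is mixed as pneumonia. Broad capture is defensible only if the row says what it captures.

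Two stronger readings are tempting. A reader might infer that the rule dilutes the ICS pneumonia signal. The documents do not support that: every modelled pneumonia comparison uses the AESI group, and no treatment ratio or test of adjudicated pneumonia is planned. A reader might also infer that non-pneumonia infections will in fact enter these counts in appreciable numbers. The documents show only that they can.

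**Conclusion.** The point holds with limited scope. A stated rule places a mixed adjudication class under a pneumonia-only name in the planned cross-check of a key ICS risk. The unlinked count may include serious infections that are not pneumonia, and a linked AESI may look corroborated when it was not. The first of these rests on reading the same two classes as the definition of the unlinked count. Both rest on the mixed class holding what its name says, with no charter sub-category applied. No hazard ratio or composite is affected, and the number of reports involved cannot be estimated from the documents. The change is worth making because it corrects what Table 3.041 reports at almost no cost.

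**What to change.** In SAP 11.5.4.2, SAP 9.2.3.1 and Table 3.041:

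- Show the linked and the unlinked counts separately for the two adjudication classes, each under its own name.
- Reserve the label adjudicated pneumonia for the exacerbation-with-pneumonia class plus any pneumonia-only sub-category that the charter provides.
- State which classes define the unlinked count.

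Do not reclassify adjudicated reports by the investigator's event term. That would make a blinded judgement depend on the source it is meant to check, and would largely empty the unlinked count by construction. Linking first by common report and falling back on the date window is not a full remedy either, because the fallback can restore the same false match. The linked rows should therefore be read as agreement in class and timing, not as confirmation of the individual event.

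The cost is SAP wording, some added rows in one table, and a smaller count labelled adjudicated pneumonia. No new data are needed. The SAP synopsis requires decisions about the final analysis to be made by Source Data Lock, so the definition should be settled by then.

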**11.5.4.3. Bone Fracture**

Bone Fracture

 
• Bone fracture event rate will be calculated in the same manner as AE rate.
 

Bone Fracture Incidents

 
• If a subject suffers fractures in multiple locations with the same date of fracture, this is
 

Bone Fracture

considered to be one fracture incident.
 
 
In the case of multiple fracture types (traumatic/non-traumatic) contributing to one fracture incident, the worst case fracture type (non-traumatic) will be assigned to the fracture incident. E.g. if a subject has a traumatic wrist fracture and a non-traumatic foot fracture on the same date, this will be considered to be one non-traumatic fracture incident.
 
Bone fracture incident event rate will be calculated in the same manner as AE rate.
 

**11.5.4.4. Maximum/Minimum Post-Baseline and Worst-Case Post-Baseline**

Maximum/Minimum Post-Baseline and Worst-Case Post-Baseline	
Definition	Reporting Details
Maximum post-baseline (QTcF, QTc B, PR interval, ECG heart rate, pulse rate, systolic BP, diastolic BP and laboratory tests)	Maximum on-treatment value over all time-points (including scheduled and unscheduled assessments)
Minimum post-baseline (Diastolic BP and laboratory tests that do not have a lower limit = 0)	Minimum on-treatment value over all time-points (including scheduled and unscheduled assessments)
Worst case post-baseline (ECG findings)	
Including scheduled and unscheduled on-treatment assessments
 
 
'Abnormal' if any on-treatment assessment is evaluated as 'Abnormal'
 
'Unable to evaluate' if all on-treatment assessments are 'Unable to evaluate'
 
'Normal' if any on-treatment assessment is evaluated as 'Normal' and there are no on-treatment assessments evaluated as 'Abnormal'
 

**NOTES :**

- The treatment phase definitions specified in Section 11.3.3 will be used and only assessments within the on-treatment period will be considered in assessment of minimum/maximum/worst-case post-baseline.
- Assessment of minimum/maximum/worst-case post-baseline will include data from scheduled, unscheduled and study treatment discontinuation visits (if applicable), and will include the Week 4 pre-dose ECG for the Pre-dose ECG sub-population. Vital signs (pulse rate, systolic BP and diastolic BP) collected at an assessment associated with a pneumonia event will also be included in derivation of a 'maximum/minimum post-baseline' assessment. The pneumonia event related assessments (e.g. vitals) dates will be assumed to be the same as the event date.

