1.3.1. Risk Assessment

Potential Risk of Clinical Significance		Mitigation Strategy
Pneumonia in patients with COPD	
Pneumonia is a class concern for any ICS-containing product for the treatment of COPD. In two replicate 12 month studies, in the FF/VI clinical program, in a total of 3,255 patients with COPD who had experienced a COPD exacerbation in the previous year, there was a higher incidence of pneumonia (6%-7%) reported in patients receiving the FF (at strengths of 50, 100, and 200 µg)/VI 25 µg combination than in those receiving VI 25 µg alone (3%). In some instances these pneumonia events were fatal (including one fatality on FF/VI 100/25 µg dose). Risk factors for pneumonia observed in these studies included current smokers, patients with a history of prior pneumonia, patients with a body mass index <25 kg/m² and patients with an FEV₁<50% predicted. These factors should be taken into consideration when using an ICS in patients with COPD. Pneumonia risk will be important in the benefit-risk assessment for FF/UMEC/VI in COPD patients, hence a robust risk mitigation strategy is being proposed.
	
 - Exclusion criteria as specified in Section 4.3 of the protocol - Collection of information on previous history of pneumonia in past 12 months, including hospitalisation at baseline - Use of pneumonia electronic Case Report Form (eCRF) - All diagnoses of pneumonia (radiographically confirmed or unconfirmed) must be reported as an AE or SAE (if applicable), as specified in Section 6.3.16 - Central CXR read required at baseline and whenever a patient has suspected pneumonia or mod/severe exacerbations during the study - Instream review of blinded data - IDMC review of unblinded data

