6.3.13. Vital Signs

Vital signs will be performed prior to taking the morning dose of IP and prior to conducting spirometry. Vital signs will be collected at Screening, Weeks 4, 28, and 52 (or IP Discontinuation Visit). Blood pressure (systolic and diastolic) and pulse rate will be measured in the sitting position after approximately 5 minutes rest. A single set of values will be collected and recorded in the source documentation and eCRF.

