
 
● Laboratory results, ECG results/findings and vital signs measurements collected as part of cardiovascular event reports will not be included in any tables, listings or any minimum/maximum post-baseline assessments.
 
	
Descriptive Summary Statistics	
Continuous Data	Refer to IDSL Statistical Principle 6.06.1
Categorical Data	N, n, frequency, %
p-value	

 
● Both adjusted and unadjusted p-values will be displayed on the primary analyses outputs for
 
	

Reporting Standards

the endpoints within the hierarchy (detailed in Section 11.9) and will be labeled 'Adjusted p-value' and 'Unadjusted p-value'
 

• All other p-values will be unadjusted and labeled purely as 'p-value'.

Time to event results

• For all time to event analyses, the first quartile and median time to event will be presented. If less than 25% of subjects experienced the event within a treatment group then the first quartile will be displayed as NA (not applicable) for that treatment. If less than 50% of subjects experienced the event within a treatment group then the median will be displayed as NA (not applicable) for that treatment.

Graphical Displays

• Refer to IDSL Statistical Principals 7.01 to 7.13.

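### Maximum vital-sign rows take in pneumonia-assessment readings but not cardiovascular-event readings, so the FF-containing arms could get more acute-illness values than UMEC/VI

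*SAP*

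**What the plan says.** Two sections of the SAP set rules for vital signs recorded in connection with an event.

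- **Pneumonia.** On how the largest and smallest post-baseline values are obtained, the notes to 11.5.4.4 say: "Vital signs (pulse rate, systolic BP and diastolic BP) collected at an assessment associated with a pneumonia event will also be included in derivation". On timing they add: "The pneumonia event related assessments (e.g. vitals) dates will be assumed to be the same as the event date".
- **Cardiovascular events.** Section 11.4.3 says that "vital signs measurements collected as part of cardiovascular event reports will not be included in any tables, listings or any minimum/maximum post-baseline assessments".

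Section 11.5.4.4 derives a maximum for pulse, systolic and diastolic pressure over scheduled and unscheduled readings. Among the vital signs, it derives a minimum only for diastolic pressure. The notes restrict the derivation by phase: "only assessments within the on-treatment period will be considered in assessment of minimum/maximum/worst-case post-baseline". Discontinuation-visit readings also count (9.2.11.1).

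Protocol 6.3.13 sets the schedule: "Vital signs will be collected at Screening, Weeks 4, 28, and 52". They are also due if a subject attends an IP Discontinuation Visit. Readings are taken with the subject seated after about 5 minutes' rest and before dosing and spirometry. A subject who completes treatment therefore has three scheduled on-treatment readings.

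On pneumonia, Protocol 1.3.1 reports that in two 12-month studies "there was a higher incidence of pneumonia (6%-7%) reported in patients receiving the FF". The treatment meant is FF/VI, and the figure on VI alone was 3%. The protocol calls pneumonia a class concern for any ICS-containing product.

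**The concern.** The pneumonia readings are additional measurements that exist only in subjects who fell ill. They are taken during an illness whose confirming signs include fever, tachypnea and hypoxemia (Protocol 6.3.16). If pneumonia is more frequent with FF, the number of chances to record a high value depends on treatment arm, and the extra values differ in kind from the seated, rested, scheduled ones.

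Protocol 1.3.1 lists heart rate and blood pressure assessments among the mitigations for cardiovascular effects of UMEC and VI. The only descriptive vital-signs tables in the SAP display list are 3.067 and 3.068. A reader who sees a higher maximum pulse there on FF/UMEC/VI or FF/VI than on UMEC/VI could take it for a cardiovascular effect when part of it is an ICS-related pneumonia excess.

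The dating rule adds a little. A reading taken after the on-treatment window still counts if pneumonia onset fell by the treatment stop date + 1 (SAP 11.3.3.3).

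**Working it through.** The plan gives no figure for this quantity, so there is nothing to reproduce. The check sizes the shift that the rule could cause.

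**Inputs from the documents**
- Pneumonia incidence: 6%-7% on FF/VI and 3% on VI alone (Protocol 1.3.1), used as a proxy for the FF-containing arms and UMEC/VI.
- Planned arm sizes: 4,000, 4,000 and 2,000.
- Scheduled on-treatment readings: three (Weeks 4, 28 and 52).

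**Assumed inputs, not in the documents**
- Mean pulse 76 bpm, between-subject SD 8.5, within-subject SD 7.
- A pulse rise in pneumonia of 0 to 30 bpm.
- One recorded pulse for every subject with pneumonia.

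**Subjects with an added reading.** 4,000 × 0.06 = 240 to 4,000 × 0.07 = 280 in each FF-containing arm. In UMEC/VI it is 2,000 × 0.03 = 60, equivalent to 120 per 4,000.

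**Formula.** Shift in mean maximum = (incidence on FF arm − incidence on UMEC/VI) × share of cases with a recorded pulse × mean lift per case. The lift is how far the extra reading raises that subject's maximum above the maximum of the three scheduled readings. It cannot be negative, so the direction follows from the incidence difference alone.

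**Result.** The table comes from a simulation of 1,000,000 subjects per scenario. The lift column is the 6% v 3% shift divided by 0.03. Without pneumonia readings, 3.61% of subjects have a maximum above 100 bpm.

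| Assumed rise (bpm) | Mean lift per case (bpm) | Shift in mean maximum, 6% v 3% / 7% v 3% (bpm) | Shift in share above 100 bpm, 6% v 3% / 7% v 3% (points) |
|---|---|---|---|
| 0 | 1.3 | 0.04 / 0.05 | 0.03 / 0.04 |
| 10 | 6.0 | 0.18 / 0.24 | 0.24 / 0.32 |
| 15 | 9.7 | 0.29 / 0.39 | 0.53 / 0.71 |
| 20 | 14.3 | 0.43 / 0.57 | 0.97 / 1.30 |
| 30 | 24.0 | 0.72 / 0.96 | 2.01 / 2.69 |

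A second set of assumptions (mean 77, SDs 8 and 7, pulse in pneumonia averaging 90-100 with SD 12, incidence 6.5% v 3%) gives 0.33-0.62 bpm, inside the same range.

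The shift is proportional to the share of cases with a recorded pulse. If half have one, every mean shift halves; for example, 0.57 becomes 0.57 × 0.5 = 0.285 bpm.

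**What is not touched.** The modelled analyses of pulse and blood pressure (SAP 9.2.13.1) use the value at each visit, so Tables 3.069-3.071 and the by-visit summaries do not change. No blood-pressure shift has been calculated, because the documents give no basis for its size or direction in pneumonia.

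**The case against.** **The two rules are not a contradiction.** A reader might infer that the SAP conflicts with itself. It does not: each rule names its own data source and can be programmed as written. What is missing is a reason for treating the two sources differently.

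**Including extremes is the cautious choice.** A maximum row is meant to capture extremes, and dropping on-treatment readings loses safety information. This stands, and it is why the fix keeps the readings visible. But caution alone does not explain the rule, since it would also keep cardiovascular-event readings. Nor does the rule always lean the cautious way: in UMEC/VI versus FF/VI, raising the FF/VI maximum could hide a UMEC effect on pulse.

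**The contrast that isolates UMEC is largely safe.** All arms contain VI, and FF/UMEC/VI versus FF/VI isolates UMEC with FF in both arms. An ICS-related excess should roughly cancel there. This stands.

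**The incidence figures are a proxy.** A reader might infer that the protocol predicts twice as much pneumonia on FF here. It does not. The figures come from earlier studies of FF 50, 100 and 200 with VI against VI alone, and no UMEC/VI rate is given. The direction is supported; the ratio is borrowed.

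**How many readings will exist is unknown.** The confirmation criteria in Protocol 6.3.16 include neither pulse nor blood pressure, and the measurement named for the pneumonia page is oximetry.

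**There may be an offset.** Unscheduled readings count too, and the design assumes more exacerbations on UMEC/VI (0.94 a year) than on FF/UMEC/VI (0.80). Readings taken during exacerbations would push the other way. The assumed gap between UMEC/VI and FF/VI is much smaller (0.94 v 0.91).

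**Cardiovascular risk is not left unreported.** A reader might infer that it is, because cardiovascular-event vital signs are dropped. The events themselves are covered by the adverse events of special interest, the time-to-first-event models and MACE (SAP 9.2.3, 9.2.4, 9.2.13.2).

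**Conclusion.** The concern holds for the descriptive maximum rows, in the comparisons of each FF-containing arm with UMEC/VI. The rule makes the number of acute-illness readings depend on pneumonia frequency, which the documents give good reason to expect to be higher with FF. The shift in mean maximum pulse is roughly 0.2-1.0 bpm, and in the share above 100 bpm roughly 0.2-2.7 percentage points on a base of about 3.6%. Both ranges rest on an assumed 10-30 bpm rise, a recorded pulse for every pneumonia, the borrowed incidence figures and no offset from exacerbation readings.

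It would go too far to say that the FF-containing arms will show a higher maximum pulse. This is a possible bias, its net size is not established, and the SAP plans no test on the maximum. No modelled result is at risk.

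**What to change.** Before unblinding, amend the notes to SAP 11.5.4.4 so that one rule applies to event-form vital signs:

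1. Derive the main maximum/minimum rows of Tables 3.067 and 3.068 from scheduled, unscheduled and discontinuation-visit on-treatment readings, without pneumonia-form values. This matches what 11.4.3 does for cardiovascular event reports.
2. Add a second row that includes the pneumonia-form values, labelled as such, with a footnote that their dates are set to the event date. No on-treatment extreme that the current rule would show is then lost.

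The cost is an SAP sentence, a data filter and one extra row per parameter. No new data collection is needed. Fixing the rule before unblinding matters because a later change could look data-driven.
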